#### **6.4.4 Unscheduled or After-Hours Visits**

Blood will be obtained by finger prick on any unscheduled day, only when a fever is documented or reported in the previous 24 hours, for thick blood smears (for parasite density and gametocytes), filter paper collection, and potential additional studies.

Parents/guardians will be encouraged to visit TDH or MGH when urgent care is needed for her or his child outside of study clinic hours. Parents/guardians will be instructed to inform hospital personnel of their child's involvement in the study at the time of registration and to visit the study clinic on the following day. If a patient is diagnosed with uncomplicated malaria outside of clinic hours, he or she will receive treatment from a hospital supply of AL and the doctors will be instructed to refer patients to our study clinic when it opens at 8 am the following day. If a patient is diagnosed with severe

malaria, he or she will receive quinine following standard TDH or MGH treatment guidelines. Patients with non-malarial illnesses will be managed at the discretion of the TDH or MGH staff. Study personnel will visit TDH or MGH daily to inquire about visits from study subjects and facilitate follow-up in the study clinic.

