### 6.3 Classification of Uncomplicated Malaria

All episodes of malaria will be classified as uncomplicated or complicated based on the following criteria:

Uncomplicated malaria (all the following must be present)

- 1) Fever ( $> 38.0^{\circ}\text{C}$  tympanic) or history of fever in the previous 24 hours
- 2) Positive thick blood smear
- 3) Absence of complicated malaria

Complicated malaria (any of the following)

- 1) Evidence of severe malaria (Appendix D) and parasitemia
- 2) Danger signs present and parasitemia
- 3) Parasite density  $> 500,000/\mu$ L

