### 6.4 Management and Follow-up of Malaria

#### 6.4.1 3-day AL regimen

Following diagnosis of malaria on Study Day 0, children managed with the 3-day AL regimen will be evaluated clinically on Study Days 1, 2, 3, (4\*), 7 (8\*), 10, 14, 21, 28, 35, 42 and on any unscheduled day in which the patient is brought to the clinic (Appendix A and B). Children who do not return for a scheduled visit will be visited by a study home visitor and, if necessary, transported to the study clinic. Blood will be obtained by finger prick on Study Days 0, 1, 2, 3, (4\*), 7, (8\*), 10, 14, 21, 28, 35, 42 and on any unscheduled day in which the patient is brought to the clinic for thick blood smears (for parasite density and gametocytes) and filter paper collection (see section 6.8).

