#### **6.4.6 Criteria and management of Early/Late Treatment Failure**

Treatment outcomes will be based on 42-day treatment outcomes as per standard WHO classification system. Interim 28-day outcomes will also be assessed. The following criteria will be used for all participants participating in intensive and/or population PK studies. Patients treated for uncomplicated malaria but classified as early or late clinical failures within 14 days of treatment will be treated with quinine. Clinical failures between days 15-42 will be treated as a new episode of malaria.

##### Early Treatment Failure: Study Days 0, 1, 2, and 3

- Development of danger signs or severe malaria on study Days 0-3 in the presence of parasitemia
- Parasitemia on study Day 2 higher than on Day 0, irrespective of temperature
- Parasitemia on study Day 3 with temperature > 38.0° C (tympanic)
- Parasitemia on study Day 3 > 25% of count on Day 0

##### LPF (Late Parasitological Failure): Days 4 to 42

- Presence of parasitemia on Days 4-42 with temperature < 38.0 ° C (tympanic) and no history of fever in past 24 hours, without previously meeting any of the criteria for early treatment failure

##### LCF (Late Clinical Failure): Days 4 to 42

- Development of danger signs or severe malaria Days 4 to 42 in the presence of parasitemia, without previously meeting any of the criteria of early treatment failure or late parasitological failure
- Temperature > 38.0 ° C (tympanic) or history of fever in past 24 hours on Days 4 to 42 in the presence of parasitemia, without previously meeting any of the criteria of early treatment failure or late parasitological failure

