## APPENDIX A. SCHEDULE OF EVALUATIONS: INTENSIVE PK STUDY

INTENSIVE PK STUDY															
Study Day	0 	1	2	3	4	5 	6 	8 	10 	14	21	28	35	42	Any other day 
ADMINISTRATIVE AND REGULATORY PROCEDURES															
Screening and study participation informed consent	X														
HIV counseling and referral if necessary 	X														
Collect locator information	X														
CLINICAL AND LABORATORY EVALUATIONS															
History 	X	X	X	X	X	X 	X 	X		X	X	X	X	X	X
Physical Examination 	X	X	X	X	X	X 	X 	X		X	X	X	X	X	X
HIV testing and documentation 	X														
Hematology and Chemistries 	4mL									4mL		4mL			
Rapid Diagnostic Test (RDT)	X							X		X	X	X	X	X	X
Thick Blood Smear  and Filter Paper collection (finger stick) for LAMP	X	X	X	X	X	X 	X 	X	X	X	X	X	X	X	X
Thin Blood Smear 	X														X
Electrocardiogram (ECG) 	X			X		X		X				X			
DRUG ADMINISTRATION															
AL dosing for all study subjects 	X	X	X	X	X 	X 									
Antiretroviral dosing for HIV-infected subjects 	X	X	X	X	X	X	X	X		X					
INTENSIVE PHARMACOKINETIC STUDY SAMPLING (VENOUS OR CAPILLARY DRAWS AS PER SECTION 6.7)															
3-day AL regimen Artemether and Lumefantrine	200µL (pre-AL) 2 and 4 hrs post-dose	200µL 2 and 4 hrs post-dose	200µL 2 and 4 hrs post-dose	500 µL (0, 0.5, 1, 2  , 3, 4, 6 and 8  hrs)  (additional 200 µL at 2 and 8 hrs)	200µL (24 hrs)			200µL (120 hrs)		200µL (288 hrs)	200µL (456 hrs)				200µL

5-day AL regimen Artemether and Lumefantrine 	200µL (pre-AL) 2 and 4 hrs post- dose	200µL 2 and 4 hrs post- dose	200µL 2 and 4 hrs post- dose	200µL 2 and 4 hrs post- dose	200µL 2 and 4 hrs post- dose	500 µL (0, 0.5, 1, 2, 3, 4, 6 and 8 hrs)	200µL (24 hrs)	200µL (120 hrs)		200µL (288 hrs)	200µL (456 hrs)				200µL
Blood for metabolomics and molecular studies	1mL			X 				X 	X 	1mL	X 	1mL	X 	1mL	1mL
APPROXIMATE TOTAL BLOOD VOLUME (mL)	5.6	0.6	0.6	0.6-4.8	0.4-0.6	0.2-4.2	0.4	0.6	0.3	5.4	0.6	5.2	0.4	1.2	1.4

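### Section 6.4.4 gives hospital AL after hours to children for whom 6.4.6 requires quinine (clinical failure through Day 14), and its fever-only smear rule conflicts with 6.4.1, 6.4.2 and Appendices A and B

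*Combined protocol and SAP*

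**What the plan says.** **Rescue drug.** Under Section 6.4.4, if a patient is "diagnosed with uncomplicated malaria outside of clinic hours, he or she will receive treatment from a hospital supply of AL", the hospital doctors then refer the child to the study clinic at 8 am. Quinine appears in that section only for severe malaria. The section gives no limit by study day and does not mention 6.4.6.

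Section 6.4.6 says that children "classified as early or late clinical failures within 14 days of treatment will be treated with quinine". For later failures it says "Clinical failures between days 15-42 will be treated as a new episode of malaria".

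Section 6.3 says "All episodes of malaria will be classified as uncomplicated or complicated based on the following criteria". The uncomplicated class needs fever or a 24-hour history of fever, a positive thick smear, and no complicated malaria. It makes no exception for a child treated a few days before.

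**Smears on unscheduled days.** Section 6.4.4 says: "Blood will be obtained by finger prick on any unscheduled day, only when a fever is documented or reported in the previous 24 hours". Section 6.4.1 takes finger-prick blood "on any unscheduled day in which the patient is brought to the clinic for thick blood smears", and 6.4.2 has the same rule for the 5-day regimen. In Appendices A and B, the row for thick smear "and Filter Paper collection (finger stick) for LAMP" is marked under every column, including the one for any other day, with no fever condition.

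**The concern.** The first conflict concerns the rescue drug. Late clinical failure needs only parasitemia with fever or a history of fever, so most such children also count as uncomplicated malaria under 6.3. Hospital staff who follow 6.4.4 give AL, while 6.4.6 requires quinine. At worst, a child who has just failed AL starts rescue on AL. In the 5-day arm on Days 3-4, and in either arm on Day 2, the randomised course may still be running. Section 6.4.4 does not say whether the hospital dose replaces it, adds to it, or ends it.

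The second conflict concerns ascertainment. Late parasitological failure is afebrile by definition, so the fever-only rule cannot detect it at an unscheduled visit. Recurrent malaria by Day 42 is a primary outcome (9.2.1), and recurrence is analysed with Cox models (9.5.2), so the date of detection matters. If fever develops before the next smear, the child is recorded as a late clinical failure. Section 6.4.6 limits that class to children "without previously meeting any of the criteria of early treatment failure or late parasitological failure".

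**Working it through.** **Step 1: rescue drug by study day.** The child has no danger signs or severe malaria, has a positive smear and fever or a history of fever (so is uncomplicated under 6.3), and is seen after hours.

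| Study day and finding | 6.4.4 | 6.4.6 | Conflict |
|---|---|---|---|
| Days 0-1 | AL | No failure criterion met | No quinine rule applies |
| Day 2, parasitemia above Day 0 | AL | Early failure: quinine | Yes |
| Day 3, temperature above 38.0 C | AL | Early failure: quinine | Yes |
| Day 3, count above 25% of Day 0 | AL | Early failure: quinine | Yes |
| Day 3, history of fever only, count at or below 25% | AL | No failure criterion met | No quinine rule applies |
| Days 4-14, fever or history of fever with parasitemia | AL | Late clinical failure: quinine | Yes |
| Days 15-42 | AL | New episode | No |

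For severe malaria, 6.4.4 gives quinine, and 6.4.6 does so too within 14 days, so there is no conflict.

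**Step 2: limits on exposure.** Section 6.4.4 refers the child to the clinic at 8 am and has study staff visit the hospitals daily. Section 3.3 has families ask for an on-call study physician after hours at TDH. For MGH it gives opening hours only, and 6.4.4 does not mention the role. About one AL dose before study classification is a reasonable reading.

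**Step 3: does that dose matter for PK?** Inputs are the Table 1 (1.1.4) values, comparing HIV-uninfected children with children on EFV: Day 7 level 340 and 111; Day 14 level 86 and below quantification; half-life 64.3 and 23.7; AUC 270 and 130.

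Assumptions: the table as read shows no units, so levels are taken as ng/mL, half-life as hours and AUC as ug*h/mL. The Day 8 level equals the Day 7 value. One dose on the evening of Day 10 adds one sixth of the Day 7 value at Day 14. The last sample is Day 14. The log-down trapezoid of 9.4.2 runs over 144 h, and the tail is level x half-life / ln 2.

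- EFV, without the dose: 111 x 23.7 / ln 2 = 3,795.
- EFV, with the dose (Day 14 level 111/6 = 18.5): 144 x (111 - 18.5) / ln 6 + 18.5 x 23.7 / ln 2 = 7,434 + 633 = 8,067. The difference is about 4,271, and 4,271 / 130,000 = 3.3%.
- Uninfected, without the dose: 144 x (340 - 86) / ln(340/86) + 86 x 64.3 / ln 2 = 34,586.
- Uninfected, with the dose (86 + 56.7 = 142.7): 144 x (340 - 142.7) / ln(340/142.7) + 142.7 x 64.3 / ln 2 = about 45,955. The difference is 11,369, and 11,369 / 270,000 = 4.2%.
- One such child of average AUC in an arm of 30: 3.3/30 = 0.11% and 4.2/30 = 0.14% of the arm mean. Section 9.4.1 powers the study for a 35% difference.

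Day 21 is not assured for these children. The 28-day rules (3.2.3, 4.2) bar re-enrolment, and 6.4.6 aims to follow them for about 7 days (Day 10 + 7 = Day 17). Even tripling the larger figure gives 3 x 0.14 = 0.42%.

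**Step 4: smear rule.** The smear row in Appendix A has 15 marks for 15 columns, and in Appendix B 14 marks for 14 columns. The last mark in each is the any-other-day column. Footnote 10 calls this a sick visit, but it makes only the PK sample conditional, on a positive smear. From Day 14, scheduled smears are 7 days apart. A smear skipped on Day 15 waits until Day 21, which is 6 days. Smears fall on Days 28 and 42, so a delay within one week does not carry detection past either time point if parasitemia persists and the visit is kept.

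**The case against.** The strongest defence is that 6.4.4 is interim care. Section 6.4.6 acts on children already classified as failures, and that takes study-day criteria and, for some, the Day 0 count. The hospital doctor has neither, and the child reaches the study clinic in the morning. This stands as a limit on harm. It does not remove the conflict, because 6.4.4 states no exception for recently treated children and no switch to quinine.

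On smears, 6.4.4 could be read as the specific rule that qualifies 6.4.1 and 6.4.2. Weekly smears continue in any case, and there is no separate endpoint for parasitological against clinical failure. That limits the consequence, but the two rules still cannot both be followed.

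A reader might infer more than the documents support:

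- **That children are left on a failing drug.** The morning referral argues against this.
- **That most failures are affected, because the clinics are closed 15 of every 24 hours.** That is clock time, not the share of failures presenting then. The documents give no such share.
- **That the AUC comparison is biased.** Step 3 shows that it is not, to any extent that matters.
- **That every febrile, smear-positive child through Day 14 should get quinine.** Children on Days 0-3 who meet no failure criterion are still under treatment, and quinine would end their randomised course without cause.

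**Conclusion.** Both contradictions are in the current text and should be fixed. The drug conflict is confined to children without danger signs or severe malaria who are seen after hours and meet one of these criteria: Day 2 parasitemia above Day 0; Day 3 parasitemia with temperature above 38.0 C or above 25% of the Day 0 count; or fever or history of fever with parasitemia on Days 4-14. Its likely size is about one AL dose per affected child. That rests on the morning referral working as described. The number of such children cannot be estimated from the documents.

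The case rests on a clear rescue instruction, not on PK. The AUC figures depend on the assumptions listed and serve only to show that the group comparison is safe. The smear conflict can delay detection of afebrile parasitemia by up to 6 days at an unscheduled visit. The frequency of such visits is not given, so the effect on the recurrence analysis cannot be sized.

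**What to change.** Amend Section 6.4.4 as follows.

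- A study child seen after hours who meets a 6.4.6 early or late clinical failure criterion through Day 14 receives quinine.
- The on-call study physician is contacted at both TDH and MGH to classify the episode. Any remaining study AL stops only when that classification is made.
- A child on Days 0-3 who meets no failure criterion continues the randomised AL course.
- Hospital AL under 6.4.4 applies from Day 15.

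Use one smear rule throughout: a smear at any unscheduled clinic visit, as 6.4.1, 6.4.2 and the appendices already have it. A sentence in 9.4.2 excluding lumefantrine samples taken after non-study AL is optional.

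The cost is a cross-reference and a few sentences, an on-call arrangement stated for MGH, and an instruction to two hospitals that already give quinine for severe malaria. It also means a few more finger-prick smears, which the appendices already schedule.

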#### **6.4.5 Missed or late visits**

Parents/guardians/participants will be instructed to return on specified follow-up days in all studies. If a participant fails to return on the appropriate follow-up day, a home visitor will be sent to assist them in returning to the clinic as soon as possible for follow-up.

#### **6.4.6 Criteria and management of Early/Late Treatment Failure**

Treatment outcomes will be based on 42-day treatment outcomes as per standard WHO classification system. Interim 28-day outcomes will also be assessed. The following criteria will be used for all participants participating in intensive and/or population PK studies. Patients treated for uncomplicated malaria but classified as early or late clinical failures within 14 days of treatment will be treated with quinine. Clinical failures between days 15-42 will be treated as a new episode of malaria.

##### Early Treatment Failure: Study Days 0, 1, 2, and 3

- Development of danger signs or severe malaria on study Days 0-3 in the presence of parasitemia
- Parasitemia on study Day 2 higher than on Day 0, irrespective of temperature
- Parasitemia on study Day 3 with temperature > 38.0° C (tympanic)
- Parasitemia on study Day 3 > 25% of count on Day 0

##### LPF (Late Parasitological Failure): Days 4 to 42

- Presence of parasitemia on Days 4-42 with temperature < 38.0 ° C (tympanic) and no history of fever in past 24 hours, without previously meeting any of the criteria for early treatment failure

##### LCF (Late Clinical Failure): Days 4 to 42

- Development of danger signs or severe malaria Days 4 to 42 in the presence of parasitemia, without previously meeting any of the criteria of early treatment failure or late parasitological failure
- Temperature > 38.0 ° C (tympanic) or history of fever in past 24 hours on Days 4 to 42 in the presence of parasitemia, without previously meeting any of the criteria of early treatment failure or late parasitological failure

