## **6.8 Parasitology Laboratory Studies**

**Thick blood smears.** Parasite counts (asexual stage and gametocyte counts) via blood smears will be collected in all participants on each day of clinical follow-up. In addition, in a subset of population PK participants, more frequent thick blood smears will be collected to document the rate of parasite clearance, as we have done in prior studies.

Thick blood smears will be stained with 2% Giemsa and read by experienced laboratory technologists who are not involved in direct patient care. Parasite densities will be calculated by counting the number of asexual parasites per 200 leukocytes (or per 500 leukocytes, if the count is <10 asexual parasites/200 leukocytes), assuming a leukocyte count of 8,000/ $\mu$ L. A blood smear will be considered negative when the examination of 100 high power fields does not reveal asexual parasites. Gametocytemia will also be determined by thick blood smears. At varied time points, blood smears for the determination of parasitemia will be obtained by simultaneous venous and capillary blood draws. Parasitology studies will be performed in the laboratory of [name] at Yale School of Public Health

**LAMP** will be done using a commercially available DNA amplification kit (such as the Loopamp Plasmodium Kit, Eiken, Japan). LAMP will be performed on dried blood spot specimens during each day of 42-day follow-up (See SOE). All LAMP will be run at our laboratory on the TDH clinic or Yale by those trained in LAMP.

**Rapid Diagnostic Test.** The Alere™ Malaria Ag P.f., will be prepared and used per manufacturer's instructions ([www.alera.ecom/malaria-POC](http://www.alera.ecom/malaria-POC)). A drop of capillary whole blood obtained by finger prick will be placed onto the RDT well, along with control buffers, and read according product insert. The total time for preparation and resulting is estimated at 20 minutes.

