## APPENDIX E. WHO MALARIA TREATMENT OUTCOME

ETF (Early Treatment Failure): Days 0, 1, 2, and 3
 

• Development of danger signs or severe malaria on Days 0-3 in the presence of parasitemia

• Parasitemia on Day 2 higher than on Day 0, irrespective of temperature

• Parasitemia on Day 3 with temperature > 38.0 C (tympanic)

• Parasitemia on Day 3 > 25% of count on Day 0

LPF (Late Parasitological Failure): Days 4 to 42
 

• Presence of parasitemia on Days 4-42 with temperature < 38.0 C (tympanic) and no history of fever in past 24 hours, without previously meeting any of the criteria for early treatment failure

LCF (Late Clinical Failure): Days 4 To 42
 

• Development of danger signs or severe malaria Days 4 to 42 in the presence of parasitemia, without previously meeting any of the criteria of early treatment failure or late parasitological failure

• Temperature > 38.0 C (tympanic) or history of fever in past 24 hours on Days 4 to 28 in the presence of parasitemia, without previously meeting any of the criteria of early treatment failure or late parasitological failure

ACPR (Adequate Clinical and Parasitological Response)
 

• Absence of parasitemia on Day 42, irrespective of temperature, without previously meeting any of the criteria of early treatment failure, late clinical failure, or late parasitological failure

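### As defined, a child with an afebrile positive smear on or after Day 4 can never become a late clinical failure, even if febrile or severe malaria follows by Day 42

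*Combined protocol and SAP*

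**What the plan says.** Section 6.4.6 gives two routes to LCF. The first reads "Development of danger signs or severe malaria Days 4 to 42 in the presence of parasitemia, without previously meeting any of the criteria" and goes on to name early treatment failure (ETF) and LPF. The second is fever or a fever history on those days, again only "in the presence of parasitemia, without previously meeting any of the criteria of early treatment failure or late parasitological failure". Appendix E carries the restriction in both of its LCF bullets: "without previously meeting any of the criteria of early treatment failure or late parasitological failure".

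LPF in 6.4.6 is parasitaemia on Days 4–42 with temperature below 38.0 °C "and no history of fever in past 24 hours, without previously meeting any of the criteria for early treatment failure". Only an earlier ETF blocks it.

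Smears do not depend on symptoms. Section 6.8 states: "Parasite counts (asexual stage and gametocyte counts) via blood smears will be collected in all participants on each day of clinical follow-up".

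Treatment in 6.4.6 follows the clinical label. Patients "classified as early or late clinical failures within 14 days of treatment will be treated with quinine", and "Clinical failures between days 15-42 will be treated as a new episode of malaria". Neither sentence mentions LPF.

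The case definition (trial schema and section 6.3) requires fever or a recent fever history with a positive smear, or complicated disease. Section 9.2.1 names recurrent malaria by Day 42 as a primary outcome. Section 9.5.2 models recurrent infection at Days 28–42 using the WHO outcome classes and does not say which of them are events.

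**The concern.** The rule lets the milder finding pre-empt the worse one. A routine smear that is positive in a well child fixes the class as LPF. Fever or severe malaria a week later cannot change it, and no section moves a child from LPF to LCF. The reverse order is not blocked.

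What is at stake is whether the WHO classes can represent clinical malaria. The protocol defines malaria by fever or complicated disease, yet a recurrence first seen on an afebrile smear has no clinical class and no clinical date. A time-to-event analysis built on these classes could not recover that date. The treatment sentences in 6.4.6 share the problem: a child who is LPF on Day 7 and febrile on Day 10 falls outside their wording.

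**Working it through.** The plan gives no figure to reproduce. The check applies the 6.4.6 definitions to example sequences and then applies the wording proposed under the fix.

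| Parasitaemic findings | As written | Proposed wording |
|---|---|---|
| Day 21 afebrile, Day 28 febrile | LPF only (Day 21) | LCF; first positive smear Day 21, first clinical date Day 28 |
| Day 21 afebrile, Day 28 severe | LPF only (Day 21) | LCF; same two dates |
| Day 14 febrile, Day 21 afebrile | LCF (Day 14) and also LPF (Day 21) | LCF |
| Day 2 afebrile, not ETF; Day 28 febrile | LCF (Day 28) | LCF |
| Day 3 afebrile, not ETF; Day 28 severe | LCF (Day 28) | LCF |

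Rows 1 and 2 show the block and row 3 the asymmetry. Rows 4 and 5 show its limit: afebrile parasitaemia before Day 4 is not LPF and blocks nothing.

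**Completeness.** Take seven visits (Days 4, 7, 14, 21, 28, 35, 42), each negative, afebrile-positive, febrile-positive or severe-positive. Suppose the first positive finding is afebrile and a febrile or severe one follows later. With r visits remaining after the first positive, there are 4^r − 2^r such paths. Summing over r = 0 to 6 gives 5461 − 127 = 5334. None is assigned LCF as written. This follows from the wording and says nothing about frequency.

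**Effect on the event definition** (row 1):
- If only LCF counts, the child has no event.
- If LPF or LCF counts, the event is on Day 21, when the child did not meet the section 6.3 case definition.
- If the event is malaria by section 6.3, it is on Day 28, and the classes do not hold that date.

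**Smear schedules by regimen** (6.4.1, 6.4.2, Appendices A and B):
- Intensive study: both regimens have Day 4; Days 5 and 6 are for the 5-day regimen only.
- Population study: 6.4.2 lists Days 4 and 5 for the 5-day regimen and 6.4.1 lists neither for the 3-day regimen. Appendix B marks both days without limiting them to one regimen.
- From Day 8 (intensive) or Day 7 (population), the schedules match.

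**Temperature boundary.** LPF needs a reading below 38.0 °C and no fever history; LCF needs a reading above 38.0 °C or a fever history. A parasitaemic child at exactly 38.0 °C with no fever history and no danger signs or severe disease is in neither class.

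**The case against.** The strongest defence is that the classes record the first failure, which is a legitimate convention. After LCF the child is treated and index follow-up in effect ends, so a later LPF hardly matters. The primary outcome is not LCF: section 9.2.1 speaks of recurrent malaria, section 9.5.2 of recurrent infection, and section 9 plans no LCF-only endpoint. The child also remains a failure, because Appendix E denies adequate clinical and parasitological response (ACPR) to anyone who met LPF.

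Much of this stands, and it rules out several stronger readings that a reader might infer.
- **Primary events are lost.** Not established. If LPF counts, the child is already an event, dated to the first positive smear.
- **Severe recurrences go unseen.** Not supported. Section 6.3 classifies every episode as uncomplicated or complicated, 6.4.6 provides for re-enrolment or further follow-up after recurrent malaria, and section 8.0 captures serious events.
- **The loss differs by regimen throughout follow-up.** It could differ only through the Day 4–6 smears.
- **A number of affected episodes can be given.** One could take the 47% recurrence in section 9.5.1, apply it to 80 episodes (0.47 × 80 = 37.6), and multiply by an assumed fraction caught on an afebrile smear first. The documents give no interval from patent parasitaemia to fever and no distribution of onset times, and they do not say that the 47% were febrile.

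The first-failure reading still does not rescue the rule. The named outcome is recurrent malaria, the case definition is clinical, and the 6.4.6 treatment sentences use the clinical-failure label. LPF also has no stated treatment that would end follow-up, so a later febrile episode remains possible.

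**Conclusion.** The point holds as a defect of definition. Under 6.4.6 and Appendix E, afebrile parasitaemia on Days 4–42 permanently bars LCF, including for danger signs or severe malaria, while LCF does not bar LPF. The loss is the clinical-failure label and its date, not failure status under Appendix E.

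Its effect on the primary outcome depends on which classes count as events, and sections 9.2.1 and 9.5.2 leave that open. A difference between regimens is possible only through the extra early smears: a residual afebrile positive on Day 5 or 6 in the intensive study would make a 5-day child LPF where a 3-day child has no scheduled smear. The documents do not support a count of affected episodes. The conclusion rests on the literal wording, which is the same on this exclusion in both places. It should be corrected before outcomes are coded, because in an open-label trial a later choice could look data-driven.

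**What to change.** In both 6.4.6 and Appendix E:

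1. Define LCF as febrile or complicated parasitaemia on Days 4–42 without prior ETF, whether or not an afebrile positive smear came first. Use the same day range in both places; the febrile bullet in Appendix E now stops at Day 28, a separate inconsistency.
2. Define LPF as afebrile parasitaemia on Days 4–42 in a child who meets neither ETF nor LCF by Day 42.
3. Assign a reading of exactly 38.0 °C to one class.

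For the time-to-event analysis, derive two dates per episode: the first positive smear from Day 4, and the first febrile or complicated parasitaemia. State in sections 9.2.1 and 9.5.2 which classes and which date define the event.

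The treatment sentences in 6.4.6 are keyed to clinical failure, so the sponsor must reconcile them with the revised classes. No management rule is proposed here.

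The cost is wording in two places and one derivation rule. Temperature, fever history and smears are already collected. The small downside is that some episodes counted as LPF become LCF.
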